9.4.6.3.2 Dose Modifications, Interruptions and Delays

9.4.6.3.2.1 Pegloticase Modifications

In the event of potential IR safety signals identified during the pegloticase infusion, or when the pre-infusion sUA level is >6 mg/dL, additional IR mitigation approaches, such as a slower pegloticase infusion rate, can be implemented.

Infusion of pegloticase will be immediately held if the subject experiences any significant IR such as respiratory distress, agitation, chest or back pain, urticaria or another clinically significant event occurring during infusion. If the AE meets the definition of an SAE for IR, the infusion should not be restarted unless the site Investigator determines it is safe to do so. If the AE does not meet the definition of an SAE for IR, the site Investigator may make the decision to re-start the infusion depending upon the nature and severity of the AE.

Infusions subsequent to an IR in an individual subject may be at a slower infusion rate. An example of an \sim 150-minute infusion procedure in 250 mL volume (relative to the standard steady rate over 120 minutes) that can be implemented at the discretion of the Investigator is presented in Table 9.1.

Table 9.1 Sample Pegloticase Infusion Rate Modification Following an Infusion Reaction

Time Interval	Staggered Rate (Over \sim 150 Minutes)	Standard Steady Rate (Over 120 Minutes)
First 30 minutes	1.0 mL/min (30 mLs)	2.08 mL/min
Second 30 minutes	1.5 mL/min (45 mLs)	2.08 mL/min
Third 30 minutes	2.0 mL/min (60 mLs)	2.08 mL/min
Fourth 30 minutes	2.0 mL/min (60 mLs)	2.08 mL/min
Last 27.5 minutes	2.0 mL/min (55 mLs)	Done

Alternatively, a larger volume of diluent, not to exceed 500 mL can be used. In this case, the infusion duration will be extended to a minimum of 3 hours. The total volume and duration of infusion will be captured in the medical record and eCRF.

Infusion of pegloticase may be held or delayed if the subject has an ongoing SAE or AE/SAE that occurs prior to the infusion. The status of subjects with skipped infusions will be discussed with the Investigator and the Sponsor's Medical Monitor on a case-by-case basis to determine whether the subject should continue to the next scheduled infusion or proceed to the End of Pegloticase Visit.

If a confirmed anaphylaxis event occurs in any subject, further dosing with pegloticase for that subject will be discontinued.

9.4.6.3.2.2 MTX Dose Titration Algorithm and Intolerance Criteria

During the MTX Run-in Period, a subject will be considered an MTX Run-in Screen Failure if any of the following new laboratory findings (repeat laboratory tests may be needed to confirm the findings) or symptoms reflecting MTX intolerance occur:

1. Abnormal hematology findings:
 - a. White blood cell count $<3.5 \times 10^9/\text{L}$;
 - b. Platelet count $<75 \times 10^9/\text{L}$; and
 - c. Hematocrit $<32\%$.
2. Abnormal hepatic function findings:
 - a. AST/ALT $>1.5 \times$ upper limit of reference range and
 - b. Albumin $<$ lower limit of reference range.
3. Abnormal renal function: eGFR $<30 \text{ mL/min}/1.73 \text{ m}^2$ (as estimated with the MDRD equation).
4. New clinically important signs and symptoms, such as the following:
 - a. Rash or oral ulceration;
 - b. Persistent nausea, vomiting and diarrhea;
 - c. New or increasing dyspnea or dry cough or unexplained cough with fever;
 - d. Severe sore throat, abnormal bruising; and
 - e. Severe headaches, fatigue and problems concentrating.

In addition, during the MTX Run-in Period, if minor clinical symptoms emerge, such as mild stomatitis or mild gastrointestinal discomfort, the Investigator may increase the folic acid dose from 1 mg/day to 2 mg/day and/or reduce the MTX dose (but to no less than 15 mg/week). If symptoms improve, the subject will not be considered a screen failure on the basis of that symptom.

During the Pegloticase + MTX Treatment Periods, MTX dose guidance based on new laboratory findings or new symptoms will be as follows:

Table 9.2 Methotrexate Dose Guidance Based on New Laboratory Findings or New Symptoms

Parameter/Finding	Value	Methotrexate Dose Change
White blood cell count	≥ 3.0 to $<3.5 \times 10^9/L$	Decrease from 25 mg to 20 or 15 mg OR Decrease from 15 mg to 10 mg
	$<3.0 \times 10^9/L$	Decrease to 7.5 mg or temporary stop at discretion of the Investigator
Platelet count	≥ 50 to $<75 \times 10^9/L$	Decrease from 25 mg to 20 or 15 mg OR No change if on 15 mg
	$<50 \times 10^9/L$	Decrease to 7.5 mg or temporary stop at discretion of the Investigator
Hematocrit	$<27\%$	Decrease to 7.5 mg or temporary stop at discretion of the Investigator
Alanine aminotransferase/ aspartate aminotransferase	>1.5 to $\leq 2 \times \text{ULN}$	Decrease from 25 mg to 20 or 15 mg OR Decrease from 15 mg to 10 mg
	$>2 \times \text{ULN}$	Decrease to 7.5 mg or temporary stop at discretion of the Investigator
Estimated glomerular filtration rate	$\geq 30 \text{ mL/min}/1.73 \text{ m}^2$ to $<45 \text{ mL/min}/1.73 \text{ m}^2$	Decrease from 25 mg to 20 or 15 mg OR No change if on 15 mg
	$<30 \text{ mL/min}/1.73 \text{ m}^2$	Decrease to 7.5 mg or temporary stop at discretion of the Investigator
New clinically important symptoms/signs ¹	Yes	Decrease to 7.5 mg or temporary stop at discretion of the Investigator

ULN = upper limit of normal

1. Rash or oral ulceration; persistent nausea, vomiting and diarrhea; new or increasing dyspnea or dry cough, or unexplained cough with fever; severe sore throat, abnormal bruising; severe headaches, fatigue, and problems concentrating; any other important medical event that might increase methotrexate toxicity or pre-dispose to new or worsening infection (e.g., surgery, hospitalization, treatment with antibiotics, clinical infection, developing new clinically significant pericardial/pleural effusion or ascites).

In addition, the Investigator may increase the folic acid dose from 1 mg/day to 2 mg/day. If, after more than 1 week of taking 2 mg/day folic acid, the sign/symptom or laboratory abnormalities do not resolve or improve, the subject is allowed to switch to oral leucovorin at 10 mg/week, given 10 to 24 hours POST each MTX injection, at discretion of the Investigator. In such case, the Investigator should discuss the timing of oral leucovorin administration relative to the MTX injection with the Medical Monitor to ensure subject compliance. Leucovorin taken before, at the time of or too soon (<8 hours) after MTX injection will likely reduce the efficacy of MTX.

Investigators should discuss the emergence of any 1 of the following criteria with the Medical Monitor to review the case:

1. ALT/AST $>1.5 \times \text{ULN}$ on 3 of any 5 consecutive measures;
2. Albumin $<0.8 \times$ lower limit of normal on 2 consecutive measures; and

3. Any laboratory or clinical symptoms leading to temporary stop on 3 consecutive measures, in which case the Medical Monitor will review to consider re-initiation, a continued temporary stop, or a permanent stop in discussion with the Principal Investigator.

Guidance for increasing MTX back towards 15 or 25 mg/week after dose reduction, based on improvement or resolution of abnormal liver enzymes ($>2 \times \text{ULN}$):

1. When liver enzymes return to $\leq 1.5 \times \text{ULN}$, increase MTX dose to the next available higher dose provided (i.e., 7.5 to 10 mg, 10 to 15 mg, 15 to 20 mg or 20 to 25 mg) and reassess in 2 weeks.
2. If liver enzymes remain $\leq 1.5 \times \text{ULN}$, increase MTX dose to the next available higher dose provided (i.e., 10 to 15 mg, 15 to 20 mg or 20 to 25 mg) and reassess in 2 weeks.

Improvement of other laboratory abnormalities potentially attributed to MTX may also warrant titration back up to 15 or 25 mg weekly, based on Principal Investigator judgement and in discussion with the Sponsor Medical Monitor.

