9.4.9.2 Infusion Reaction Treatment

Subjects must be monitored closely for signs and symptoms of IRs. In the event of an IR, the infusion should be slowed or stopped, and restarted at a slower rate at the discretion of the Investigator. If a serious IR occurs, the infusion should be discontinued and treatment should be provided, as needed.

If a subject experiences an AE suspected to be an IR:

- A physical examination will be performed to capture medically relevant details, including, but not limited to, a thorough dermatologic examination for detection of erythema, urticaria (hives) or peri-oral or lingual edema; a chest examination for breath sounds, stridor or wheezing; and a cardiac examination with attention to irregular heartbeat.
- Vital signs (sitting or supine blood pressure, heart rate, respiratory rate and body temperature) will be captured at least every 30 minutes until the resolution or stabilization of the AE.
- A serum sample will be collected in a serum-separator tube at that time or at the subsequent visit. The sample will be centrifuged, frozen at -20°C or colder and stored for the batch shipment to a Horizon designated laboratory for evaluation of pegloticase antibodies at a future date.
- When possible, a 12-lead electrocardiogram (ECG) will also be performed at the time of IR.

If, in the Investigator's opinion, the subject is experiencing an anaphylactic reaction (see [Section 9.5.4.1.1.5](#)), pegloticase should be immediately discontinued. Any incidence of anaphylaxis should be reported as an SAE.

The Investigator may administer any medically indicated pharmacologic agent or procedure intended to relieve symptoms (CAUTION: no other drugs can be mixed in the pegloticase infusion bag). Signs and symptoms of the AE and drugs given for treatment are to be recorded in the medical record and in the eCRF.

After the first incidence of an IR that does not meet the anaphylaxis criteria (see [Section 9.5.4.1.1.5](#)) or does not meet serious criteria, the Investigator may elect to initiate the next infusion at a slower rate. All changes to infusion rate or dilution are to be recorded in the medical record and in the eCRF.

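### For a serious infusion reaction short of anaphylaxis, one protocol section lets the Investigator restart the infusion; another discontinues it and states no exception

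*Protocol*

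**What the plan says.** Two protocol sections govern what a site does with the infusion when an IR occurs.

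**Section 9.4.6.3.2.1 (Pegloticase Modifications).** Any significant IR leads to an immediate hold. If the event qualifies as an SAE, "the infusion should not be restarted unless the site Investigator determines it is safe to do so". If it does not, "the site Investigator may make the decision to re-start the infusion depending upon the nature and severity of the AE". On later dosing: "Infusions subsequent to an IR in an individual subject may be at a slower infusion rate". On anaphylaxis: "If a confirmed anaphylaxis event occurs in any subject, further dosing with pegloticase for that subject will be discontinued".

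**Section 9.4.9.2 (Infusion Reaction Treatment).** For an IR in general, "the infusion should be slowed or stopped, and restarted at a slower rate at the discretion of the Investigator". The next sentence reads: "If a serious IR occurs, the infusion should be discontinued and treatment should be provided, as needed". If the Investigator believes the event is anaphylaxis, pegloticase is stopped at once. On later dosing, the section takes a first IR that falls short of the anaphylaxis criteria and continues "or does not meet serious criteria, the Investigator may elect to initiate the next infusion at a slower rate".

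**Section 9.4.6.2 (Determination of Dose Volume)** also bears on this. It names a serious IR as an example of a signal after which a slower rate can be used, and it allows a larger diluent volume for infusions after an IR, with no limit by seriousness.

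The SAP contains no rule on restarting an infusion or on dosing after a serious IR.

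**The concern.** During an acute event the site needs one instruction. For a serious, non-anaphylactic IR the protocol gives two: one leaves room for a restart on the Investigator's judgment, the other does not. A site that restarts under the first section departs from the second.

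The setting makes this more than an editorial matter. All subjects have already stopped pegloticase once, for lost response or a mild IR. Section 7.2 itself raises the possibility of more severe IRs on retreatment; it reports that about 66% of Phase 3 subjects with more than one IR had a second of the same or lower severity, which leaves about 34% with a worse one. Cohort 2 can include subjects with a prior IR, although only a clinically mild one reviewed by a sponsor committee; prior moderate or severe IRs are excluded.

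There is a secondary statistical stake. The composite secondary endpoint counts IRs that lead to stopping treatment (Protocol Section 9.6.1.2; SAP Section 11.4). If sites differ on whether a subject may be infused again after a serious IR, the same clinical event can count at one site and not at another.

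**Working it through.** No alpha, power or sample-size figure is involved, so the main check is a comparison of the text by type of event. It takes an IR meeting the SAE definition (9.4.6.3.2.1) and a serious IR (9.4.9.2) to be the same category.

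**Current infusion**

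| Event | 9.4.6.3.2.1 | 9.4.9.2 | Result |
|---|---|---|---|
| Non-serious IR | Investigator may restart | Restart at Investigator's discretion | Agree |
| Serious IR, not anaphylaxis | No restart unless judged safe | Discontinued; no exception | Conflict on the exception |
| Anaphylaxis | Further dosing stops (confirmed event) | Pegloticase stopped (Investigator's opinion) | Same direction |

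In Section 9.4.9.2, discontinuation for a serious IR directly follows a stop-and-restart rule for IRs generally. The contrast makes it hard to read *discontinued* there as a temporary hold.

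**Next infusion**

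Section 9.4.6.3.2.1 sets no limit by seriousness. Section 9.4.9.2 gives two conditions joined by *or*. Anaphylaxis must always be reported as an SAE (9.4.9.2 and 9.5.4.1.1.5), so three cases are possible:

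| First IR | Not anaphylaxis | Not serious | Slower next infusion if *or* is literal | If *and* was meant |
|---|---|---|---|---|
| Non-serious | yes | yes | offered | offered |
| Serious, not anaphylaxis | yes | no | offered | not offered |
| Anaphylaxis | no | no | not offered | not offered |

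The readings differ only in the middle row, which is the event at issue. Read literally, the second condition adds nothing, because every non-serious IR is already non-anaphylactic. That is why a reader may suspect *and* was meant. The text does not settle it.

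**Possible number of subjects**

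- Phase 3 IR rate at the 8 mg every-2-weeks regimen (Protocol Section 7.1.2): 22/85 = 25.9%. For 30 subjects: 0.259 × 30 = 7.8, about 8 with an IR.
- Serious share of IRs: not given. Assuming 10% to 25%: 0.10 × 7.8 = 0.8 and 0.25 × 7.8 = 1.9, so about 1 to 2 subjects.
- Anaphylaxis lies outside the conflict and has to come out of that count. Section 7.1.2 gives 6.5% from a post hoc review of the Phase 2 and 3 program: 0.065 × 30 = 1.95, about 2. That alone could account for every assumed serious IR.
- Range: 0 (all serious IRs are anaphylaxis) to 2 (none is).

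One subject is 1/30 = 3.3 percentage points of the composite overall and 1/10 = 10 points in a 10-subject Cohort 1. These are step sizes, not expected biases.

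**The case against.** The strongest reply is that the two sections are nearly aligned. Both default to not resuming after a serious IR, and Section 9.4.6.3.2.1 keeps serious and non-serious events apart in consecutive sentences. The protocol also does not always use *discontinuation* as final: its AE grading scale (Section 9.5.4.1.3) distinguishes temporary from permanent discontinuation of trial drug. This stands against calling the instructions opposite. It does not remove the exception that one section grants and the other omits.

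Four stronger readings are tempting, and the documents do not support them:

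- *A subject in the middle of a serious IR could be given more drug.* The hold is immediate, and a restart requires a judgment that it is safe. Anaphylaxis leads to stopping in both sections.
- *Section 9.4.9.2 bars any further infusion after a serious IR.* It does not say *only*, and a serious, non-anaphylactic IR meets the first of its two conditions. This is an ambiguity, not a second contradiction.
- *A same-day restart changes the composite.* The component is stopping pegloticase treatment, not stopping one infusion. Only decisions about later infusions reach it.
- *The restart decision drives the one-third tolerability rule.* That rule counts severe IRs and anaphylaxis, and severity is a different scale from seriousness. A restart would matter only if symptoms then recurred, since recurrence after initial improvement is part of how a severe IR is described.

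It is also fair that little new data capture is needed. Infusion times, volume, duration and rate changes are recorded, suspected IRs prompt additional eCRF pages, reasons for stopping pegloticase are collected, and SAP Section 14.1 summarizes incomplete and interrupted infusions.

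**Conclusion.** The inconsistency is real and narrow: whether the same infusion may be restarted, on the Investigator's judgment, after an IR that is serious but not anaphylaxis. Alongside it is an unresolved ambiguity about later infusions after that event. Nothing else in the protocol or SAP decides either question.

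The importance lies in subject safety at the bedside more than in the statistics. That sites would act differently is a reasonable inference, not something the documents show. The estimate of 0 to 2 of 30 rests on an assumed serious share and on rates observed without methotrexate, so it indicates only that few subjects are likely to be involved. The passages should still be reconciled, because the event is acute and the repair costs almost nothing.

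**What to change.** Reconcile Sections 9.4.6.3.2.1 and 9.4.9.2, and align Section 9.4.6.2 with them. In one place, with cross-references from the others, state for a serious, non-anaphylactic IR:

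1. what happens to the current infusion, including whether any Investigator exception applies;
2. what happens to subsequent infusions.

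Reword the next-infusion sentence in Section 9.4.9.2 so that *or* cannot be read two ways. Which rule is adopted is for the sponsor's clinical and safety teams; this review takes no position on it.

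The cost is a protocol wording clarification, with no added visits and no change to the sample size or analysis. An explicit eCRF item for same-day restart is optional, since existing fields largely cover it.

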9.4.7 Method of Assigning Subjects to Treatment Groups

All subjects will receive the same trial drugs (i.e., SC MTX and pegloticase).

Two sequential cohorts of subjects will be enrolled in this trial. Subjects who previously failed to maintain sUA response with pegloticase monotherapy and stopped pegloticase treatment without a history of pegloticase-related IR will be enrolled in Cohort 1.

The Safety Review Team will use the tolerability criteria to determine if Cohort 1 enrollment can continue, Cohort 2 enrollment can begin and whether subjects without a history of pegloticase-related clinically mild IR can enroll in Cohort 2.

Based on the safety assessment during Cohort 1, the trial can begin enrolling Cohort 2 if the pegloticase infusions are well tolerated or the trial will cease to screen and enroll new subjects if the pegloticase infusions are not well tolerated.

Subjects with a history of pegloticase-related clinically mild IR will be enrolled in Cohort 2. If the safety assessment during Cohort 2 indicates that the pegloticase infusions are not well tolerated based on pre-determined tolerability criteria or in the absence of subjects with a history of pegloticase-related clinically mild IR, the trial will continue with enrolling subjects without a history of pegloticase-related clinically mild IR.

9.4.8 Blinding

All trial drugs will be administered in an open-label fashion.

9.4.9 Prior and Concomitant Therapy

Medication history (i.e., prior medications) will include all prior gout medications, starting at the time of diagnosis and up to the Screening Visit and all other medications taken from 1 year prior

to the Screening Visit. Detailed pegloticase use history, including reason for discontinuation and associated reactions, if any, will be collected.

Concomitant medications are defined as drug or biological products other than the trial drugs (or prior gout medications) taken by a subject from Screening through the Post-Treatment Follow-up Visits. This includes other prescription medications (including preventive vaccines), over-the-counter medications, herbal medications, vitamins and food supplements. If a subject is treated with antibiotics, refer to Section [9.4.6.3.2.2](#) for monitoring guidelines.

Information about prior and concomitant medications, including those used for any duration to treat an AE, will be collected on source documents and the appropriate eCRFs at each visit. The generic name of the medication, indication, dose, unit, frequency, route of administration and start and stop dates will be recorded.

Other than restricted medications ([Section 9.4.10](#)), other medications used at the time of trial initiation may be continued at the discretion of the Investigator.

9.4.9.1 Gout Flare Treatment

An increase in gout flares is frequently observed upon initiation of anti-hyperuricemic therapy, including pegloticase. Subjects will be instructed to contact the site within 12 hours of the onset of symptoms. Gout flares will be confirmed through questioning or direct observation, as detailed in [Section 9.5.4.8](#). All subjects who experience a gout flare during the trial will be prescribed anti-inflammatory treatment (e.g., NSAID, colchicine, corticosteroids and intra-articular steroid injections), as clinically indicated or deemed necessary on an individual basis at the discretion of the Investigator. Pain medications for gout flare should be administered according to standard of care, as clinically indicated or deemed necessary on an individual basis at the discretion of the Investigator. All medications should be documented on the concomitant medication eCRF.

Colchicine will be prescribed in a medically appropriate dose range of 0.6 to 1.8 mg/day, usually dosed as 0.6 mg orally twice per day unless reduced dosing is necessitated by renal insufficiency or gastrointestinal intolerance. The precise dose and regimen of colchicine will be individualized for each subject by the Investigators and documented on the concomitant medication eCRF.

9.4.9.2 Infusion Reaction Treatment

Subjects must be monitored closely for signs and symptoms of IRs. In the event of an IR, the infusion should be slowed or stopped, and restarted at a slower rate at the discretion of the Investigator. If a serious IR occurs, the infusion should be discontinued and treatment should be provided, as needed.

If a subject experiences an AE suspected to be an IR:

- A physical examination will be performed to capture medically relevant details, including, but not limited to, a thorough dermatologic examination for detection of erythema, urticaria (hives) or peri-oral or lingual edema; a chest examination for breath sounds, stridor or wheezing; and a cardiac examination with attention to irregular heartbeat.
- Vital signs (sitting or supine blood pressure, heart rate, respiratory rate and body temperature) will be captured at least every 30 minutes until the resolution or stabilization of the AE.
- A serum sample will be collected in a serum-separator tube at that time or at the subsequent visit. The sample will be centrifuged, frozen at -20°C or colder and stored for the batch shipment to a Horizon designated laboratory for evaluation of pegloticase antibodies at a future date.
- When possible, a 12-lead electrocardiogram (ECG) will also be performed at the time of IR.

If, in the Investigator's opinion, the subject is experiencing an anaphylactic reaction (see [Section 9.5.4.1.1.5](#)), pegloticase should be immediately discontinued. Any incidence of anaphylaxis should be reported as an SAE.

The Investigator may administer any medically indicated pharmacologic agent or procedure intended to relieve symptoms (CAUTION: no other drugs can be mixed in the pegloticase infusion bag). Signs and symptoms of the AE and drugs given for treatment are to be recorded in the medical record and in the eCRF.

After the first incidence of an IR that does not meet the anaphylaxis criteria (see [Section 9.5.4.1.1.5](#)) or does not meet serious criteria, the Investigator may elect to initiate the next infusion at a slower rate. All changes to infusion rate or dilution are to be recorded in the medical record and in the eCRF.

